The honest answer is that causes of regional vulnerability are both intriguing and remain elusive. Altering their mechanisms may offer great therapeutic benefits. Yet, rational experiments to alter pathogenic mechanisms can proceed in the absence of knowing how regional vulnerability occurs. In the case of AD and PD, overlapping of clinical phenotypes and pathologies with disease progression implicates similar disease mechanisms, at least in some subjects.

SPECIFIC AIMS

The primary aim of this protocol is to test the safety and tolerability of R-Pramipexole in humans with probable AD. We will also explore changes in oxidative stress and brain metabolic consequences as a "proof of concept" exploratory aim.

Primary Aim: Assess the safety and tolerability of R-Pramipexole in probable AD. Twenty subjects with probable AD will initiate treatment with 100 mg/day of R(+) pramipexole for one month. If tolerated, the subjects will increase to 200 mg/day for one month and then 300 mg/day for the next 4 months. Participants will be contacted by phone every two weeks to determine any adverse events. They will also be examined by a physician, have their vital signs measured and have routine safety blood labs performed every two months.

Exploratory Aim: Assess the effect of R-Pramipexole on oxidative stress and brain metabolic consequences. Prior to initiation of R(+)PPX dosing, we will obtain plasma and spinal fluid for oxidative stress markers and obtain brain glucose metabolism PET scans (2FDG PET). During the last month of 300 mg/day dosing, obtain plasma and spinal fluid samples and repeat 2FDG PET scan.

PRELIMINARY DATA

R(+)pramipexole is a mitochondrially concentrated antioxidant

Pramipexole (PPX) is a benzothiazole synthesized in the 1980's as an apomorphine analogue [27]. The stereospecific synthesis yielded S(-)PPX (Figure 1), which possessed potent and full agonist actions at the D2 family of brain dopamine receptors. S(-)PPX was developed for clinical use in humans and was approved in 1997 by the FDA as Mirapex®, for treatment of Parkinson's disease symptoms due to nigrostriatal dopamine deficiency.

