Overview (see calendar of events below): After providing signed informed consent, participants will undergo a screening visit to assess study participant eligibility. Neuropsychological testing (ADAS-Cog) will be performed at baseline and every two months (visits 2, 3, 4, and End of Study (EOS)). A lumbar puncture and blood draw (for isoprostane analysis) and fluoro-deoxy-glucose positron emission tomography (FDG-PET) will be performed at baseline and after 6 months of treatment to serve as exploratory “proof of concept” measures to explore the effect of R-Pramipexole on key biological targets. Safety visits with laboratory testing and physical assessments will occur every two months. Follow up phone calls to the participants and their study partner will be conducted every two weeks during treatment to assess for possible adverse events.

Screening Visit: A screening visit will occur in the GCRC and last approximately 2 hours. Participants will be accompanied by a study partner and provide informed consent. Demographics, medical history, and medications will be collected by a study coordinator. The study coordinator will administer the mini-mental status exam, Geriatric Depression Scale and Hachinski Ischemic Scale. Vital signs will be assessed (height, weight, blood pressure, respiratory rate, temperature) and non-fasting blood and urine will be collected for routine safety labs including a chemistry panel (sodium, potassium, chloride, CO₂, BUN, glucose, calcium, total protein, total bilirubin, albumin, alkaline phosphatase, AST and ALT), hematology panel (complete blood count including differential), and a microscopic urinalysis. A study clinician will perform a physical and neurological exam and review the inclusion / exclusion criteria and AD diagnostic criteria to determine study participant eligibility.

Baseline Assessments: Baseline assessments will occur within four weeks of the screening visit and will consist of two or three visits to KUMC: 1) Cognitive testing at the KU Alzheimer and Memory Program (<1 hour), 2) FDG PET scanning in the radiology department (1.5 hours), and 3) GCRC visit for a blood draw and lumbar puncture (2 hours).

Cognitive Testing: A study psychometrician will perform a standard battery of cognitive tests on all participants utilizing the Alzheimer's Disease Assessment Scale – Cognitive subscale (ADAS-Cog). The ADAS-Cog is composed of 11 subtests of memory and language and is frequently used for clinical trials.

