Study Drug Administration: R(+)PPX is provided by the sponsor to the KUMC investigational pharmacy as the water soluble dihydrochloride salt, in the form of powder manufactured under GMP conditions by Quality Chemical Laboratories, the supplier of drug for all of [name] studies. The investigational pharmacy prepares a water solution at 10 mg/ml. This solution has been tested by the sponsor and is stable at 4 degrees for at least two months.

Treatment is initiated after the Baseline visit at 100mg a day (50 mg bid in morning and early evening) for 1 month. If tolerated, dosing will increase to 200mg a day (100 mg bid) for a second one-month interval. If at the end of four months of being on study drug, the participant is not experiencing side effects the study drug will be increased to 300mg a day (150 mg bid) where it will remain for the next 4 months. Subjects will be seen every two months for safety assessments prior to any dose escalation and will also be contacted every two weeks by phone (see below). If a participant experiences mild, non-serious adverse events possibly due to the study drug, the study clinician will determine the causality and make a decision whether to continue the study medication and at what dosage. If study drug is discontinued temporarily (>10 days), it will be titrated to the target dose with dose increases no more frequent than once a month.

Drug Accountability: Participants in the study will return any unused drug and study drug containers at each of the safety visits. Study partners will be asked to account for any missed dosages of the study drug and the reason for missing the dosing. Participants are encouraged to maintain 100 percent compliance with dosing. The study partner and the participant will be advised of their

compliance at each safety visit before the study drug is dispensed and means and measures to increase compliance will be initiated. All unused study drug and containers will be returned to the investigational pharmacy for disposal.

Phone Calls: Participants and their study partner will be contacted by the study coordinator every two weeks by phone after starting to take the study medication to review concurrent medications and adverse events.

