End-of-Treatment Assessments (Visit 5): Final outcome assessments will be completed during week 24 visit/ Visit 4 and consist of identical procedures to the baseline assessments (see above): 1) Cognitive testing at the KU Alzheimer and Memory Program (1 hour), 2) FDG PET scanning in the radiology department (1.5 hours), and 3) GCRC visit for a blood draw and lumbar puncture (2 hours). In addition the participant will have a physical/ neurological examination, safety laboratory sampling, vital signs, concurrent medications and adverse events. The participant will return all remaining study drug and containers at this visit. No additional medication will be dispensed.

End-of-Study Visit: Participants will return two weeks after completing the R(+)PPX treatment for a final physical and neurological exam and review of adverse events.

Data analysis

Primary Aim: Safety

Subject safety is the primary variable and item of greatest concern in this study. The extensive dosing experience with R(+)PPX in ALS subjects, many of whom have mild dementia, combined with its lack of detectable D2 dopamine receptor activity *in vivo* at 300 mg/day dosing, support its safety in probable AD subjects. Safety and tolerability will be evaluated by frequent contact with subjects and caregivers and lab safety studies every two months. The frequency and severity of adverse events will be examined and their potential causal relationship to the study drug (as determined by the study physician) will be assessed (the adverse events related to Mirapex [pramipexole] are listed in table 1 of appendix). This information will be used to guide dose selection and inform a more definitive safety and efficacy study. Additionally, cognitive performance data will be acquired every two months to assess the cognitive trajectory to explore possible dose-related changes in cognitive decline over the 6 months of intervention.

Exploratory Aims

Oxidative stress

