The sponsor studied S(-) and R(+) PPX in his laboratory beginning in 1997 and has clinically tested R(+) pramipexole in ALS subjects under a physician-sponsor IND since 2004. R(+)PPX is now commercially licensed and under separate development for treating ALS by Knopp Neurosciences. R(+)PPX is a brain and mitochondrially concentrated antioxidant that can be safely administered to humans at daily doses up to 300 mg/day and has no detectable DA receptor activity *in vivo*. At this dose many subjects achieved trough steady-state PPX levels of >1 μ M, predicting brain levels of >6 μ M that are clearly in the ROS scavenging and neuroprotective levels. R(+)PPX at 300 mg/day substantially improves the course of ALS in short-term studies and will enter Phase 3 testing later this year.

The present application seeks to introduce R(+)PPX treatment to subjects with early AD. In this protocol the subjects will undergo careful dose escalation from 100 mg/day to 300 mg/day R(+)PPX over 4 months. Subjects will have regular serum, combined with baseline and late treatment spinal fluid samples, assayed for isoprostanes as measures of oxidative stress. Serum and spinal fluid will also be assayed for [PPX]. As a measure of cerebral metabolism, brain 2-FDG PET scans will be obtained at baseline and after several months of dosing with 300 mg/day R(+)PPX.

The goal of the present study is to determine if R(+)PPX can be administered in high doses to probable AD subjects, and if so, whether oxidative stress is reduced and cerebral metabolism is increased. Hopefully the results from this study will justify the cost of a larger early efficacy study in probable AD.

Data Management

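### In a single-arm study with one common rising dose schedule, ADAS-Cog cannot show a dose-related change in decline apart from time, disease progression and repeat testing (minor; exploratory outcome)

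*Combined protocol and SAP*

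**What the plan says.** **Aim.** The combined protocol and SAP, under Data analysis, Primary Aim: Safety, says cognitive data will be collected every two months to follow the cognitive trajectory and "to explore possible dose-related changes in cognitive decline over the 6 months of intervention". It names no model, contrast or comparator for this, and no adjustment for progression or repeat testing.

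**Dose schedule.** Specific Aims, Primary Aim: "Twenty subjects with probable AD will initiate treatment with 100 mg/day of R(+) pramipexole for one month". Then: "If tolerated, the subjects will increase to 200 mg/day for one month and then 300 mg/day for the next 4 months". Study Drug Administration agrees on the first two steps ("If tolerated, dosing will increase to 200mg a day (100 mg bid) for a second one-month interval") but ties the step to 300 mg/day to a different time: "If at the end of four months of being on study drug". Conclusions describes "careful dose escalation from 100 mg/day to 300 mg/day R(+)PPX over 4 months". No control group, parallel dose or historical comparator is described for ADAS-Cog.

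**Assessment times.** Treatment protocol, Overview: "Neuropsychological testing (ADAS-Cog) will be performed at baseline and every two months (visits 2, 3, 4, and End of Study (EOS". Safety Visits places cognitive testing at the 8-weekly visits, that is weeks 8, 16 and 24. The Schedule of Study Procedures and Assessments puts the Baseline visit at week -2. The End-of-Study Visit, two weeks after treatment ends, lists examinations and adverse events but no cognitive test.

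**The concern.** A dose-related change can be seen only if dose varies in some way that time does not. Here the planned dose never falls during treatment and follows the same calendar for everyone. A participant's score at week 24 differs from the score at baseline because of dose, about six months of disease, and three further exposures to the same test, and nothing in the design separates these. Because no ADAS-Cog is scheduled in the 100 mg/day month, that dose is not observed at all. The only on-drug contrast is 200 against 300 mg/day, which is also an earlier-against-later contrast.

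The error could run either way. A retest gain could look like benefit at the higher dose, and ordinary decline could look like harm. Conclusions hopes that the results will justify a larger early efficacy study, so either misreading could carry into its planning.

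**Working it through.** The plan gives no power, precision or effect-size figure for ADAS-Cog, so there is nothing of its own to reproduce. The check is whether a dose effect can be estimated at all.

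**Inputs**
- Participants: 20, one arm (Specific Aims).
- ADAS-Cog weeks *t*: -2, 8, 16, 24 (Schedule; Safety Visits).
- Schedule A, dose *d* in units of 100 mg/day: 0, 2, 3, 3 (Specific Aims).
- Schedule B: 0, 2, 2, 3 (300 mg/day only after four months, per Study Drug Administration). The 200 mg/day at week 16 is an assumption: that section gives 200 mg/day for one month and states no dose for months 3 and 4.

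**Step 1. Visit as a category.** There are 20 × 4 = 80 scores. Twenty participant effects plus three visit effects give rank 23. In schedule A the dose column equals 2 × (visit 2) + 3 × (visit 3) + 3 × (visit 4); in schedule B it is 2, 2 and 3 times those indicators. Either way it is an exact combination of columns already present, so the rank with dose is still 23. More participants on the same schedule would not change this.

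**Step 2. Decline assumed linear (the favourable case).** Mean *t* is 11.5; deviations are -13.5, -3.5, 4.5, 12.5; Stt = 371. Formulas: r² = Std² / (Stt × Sdd); variance inflation = 1 / (1 - r²).

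| | Sdd | Std | r² | r | Variance inflation | SE multiple |
|---|---|---|---|---|---|---|
| A | 6.00 | 44.0 | 1936/2226 = 0.870 | 0.93 | 7.7 | √7.7 ≈ 2.8 |
| B | 4.75 | 39.5 | 1560.25/1762.25 = 0.885 | 0.94 | 8.7 | √8.7 ≈ 3.0 |

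Placing baseline at week 0 instead gives r = 0.91 and 0.92, with inflation 6.0 and 6.8. The conclusion is the same.

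**Step 3. What a null dose effect could look like.** The sizes here are assumptions, since the documents give none.
- *Retest gain of 1 point at every post-baseline test, fitted with linear time plus dose.* Dose slope = (Sdy × Stt - Sty × Std) / (Stt × Sdd - Std²), with Sty = -13.5.
  - A: Sdy = -2, so (-742 + 594) / 290 = -0.51 per 100 mg, or a 1.5-point apparent benefit at 300 mg/day.
  - B: Sdy = -1.75, so (-649.25 + 533.25) / 202 = -0.57 per 100 mg, or a 1.7-point apparent benefit.
- *Linear 3-point decline over the 26 weeks from baseline to week 24, fitted with dose only.* Slope = (3/26) × Std / Sdd.
  - A: 0.85 per 100 mg, or a 2.5-point apparent harm at 300 mg/day.
  - B: 0.96 per 100 mg, or a 2.9-point apparent harm.

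**Step 4. Departures from the schedule.** Suppose 1 to 6 of 20 participants stayed at 200 mg/day (assumed) and the rest followed A. Dose then becomes estimable, but only 0.8% to 4.0% of its variance remains after participant and visit effects. None of that variation is randomized.

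**Step 5. An EOS score.** If ADAS-Cog were also taken two weeks off drug, there would be 20 + 4 = 24 effects, and the rank with dose is still 24. Dose remains fully tied to visit.

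**The case against.** The strongest reply is that this asks too much of one exploratory phrase. The primary goal is safety and tolerability, cognition is listed among the exploratory variables, and the DSMB Charter says no protocols on efficacy in slowing progression are being considered. The plan commits to no test or decision rule, so it makes no dose-response claim. All of that stands, and it is why the point is minor. It does not make the quantity estimable: exploratory status excuses low precision, not a comparison that the design does not contain.

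The variance inflation figures also describe a linear-time model that the plan never proposes. That is fair. They show only that the most favourable assumption helps little; the main result is Step 1, which needs no such model.

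Three stronger inferences are tempting, and the documents do not support them.
- *That ADAS-Cog will guide dose selection.* The sentence on dose selection follows directly on the adverse-event analysis. The cognitive sentence comes after it as an addition.
- *That an EOS score would be analysed as on treatment.* The plan does not say how it would be handled, and the aim is confined to the six months of intervention. The calendar's ADAS-Cog row carries four marks, which fits baseline and visits 2 to 4 without EOS. Its columns are displaced in the available text, so that is an inference.
- *That everyone must receive identical doses, or that all departures are caused by adverse events.* Escalation depends on tolerability, the clinician may change the dose, and missed doses are recorded with their reasons.

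**Conclusion.** The point holds as a minor one. Under the planned schedule, dose at the ADAS-Cog visits is a function of visit alone, so the design cannot attribute any change in cognitive decline to dose. This is true under both schedules examined and does not depend on where baseline is placed. With linear decline assumed, the dose-time correlation is about 0.93 or 0.94 and the standard error of a dose slope is about 2.8 or 3.0 times what it would be if dose and time were uncorrelated. The second figure of each pair rests on the assumption about months 3 and 4. Departures from the schedule are not randomized and give no unbiased dose contrast.

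The consequence is a risk of misreading. The documents do not show that a dose decision or efficacy claim will be based on ADAS-Cog.

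**What to change.** Replace the phrase on dose-related change with: *ADAS-Cog change from baseline at weeks 8, 16 and 24 will be described by visit with 95% confidence intervals; no dose-response conclusion will be drawn because dose and time are tied.*

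Two inconsistencies should be reconciled at the same time.
- The timing of the step to 300 mg/day differs between Specific Aims and Study Drug Administration, and Conclusions describes escalation over four months. It decides which dose the week 16 score belongs to. The Study Drug Administration text, read as four months followed by four more, also gives 4 + 4 = 8 months against a 24-week treatment period.
- The Overview lists ADAS-Cog at "visits 2, 3, 4, and End of Study (EOS", while the End-of-Study Visit text does not include it and the calendar appears not to. If an EOS score is taken, report it separately as off treatment.

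The cost is one sentence of analysis text and the two reconciliations. The ADAS-Cog change itself alters no dose or sample size and keeps all the cognitive data. The sponsor gives up a dose-related reading that the design cannot support.

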The DSMB will have access to de-identified participant medical records and other study-related records. The investigator agrees to cooperate with the monitor (s) to ensure that any problems detected in the course of these monitoring visits are resolved. Personal contact between the DSMB and the investigator will be maintained throughout the clinical trial to assure that the investigator is fulfilling his obligations and the facilities used in the clinical trial remain acceptable.

The DSMB will perform a quarterly review of lab safety data, results of physical/ neurological assessments and subject adverse event/SAE reports. The DSMB can advise and recommend temporary or permanent withdrawal of a subject or that the entire study be placed on hold or terminated.

All grade 2 and above AE's according to CTCAE v3.0 will be reviewed by the DSMB members quarterly. To facilitate this review, a list of each AE grade 2 or higher (by CTCAE v3.0) will be generated from REDCap. Each AE listed will include the grade, the type of event, and the potential relationship of the AE to the study intervention. The PI will be notified within 24 hours by the study coordinator of all AE's grade 3 or higher. Should a study participant experience an AE in any category rated 3 or greater according to CTCAE v3.0, that individual will be removed from the study immediately. Should three or more subjects (15% of target enrollment) have AE's in any category that is grade 3 or higher according to CTCAE v3.0 that are possibly or probably related to study intervention, the study will be terminated.

Schedule of Study Procedures and Assessments

Week #	-4	-2	0	2	4	6	8	10	12	14	16	18	20	22	24	26
Visit Name	Scr	B	1	P/C	P/C	P/C	2	P/C	P/C	P/C	3	P/C	P/C	P/C	4	EOS
Informed Consent	X															
NINDS-ADRDA	X															
Hachinski Ischemic Scale	X															
Geriatric Depression Scale	X															
MMSE	X															
Demographics	X															
Medical History	X	X														
Medication History	X	X														
Body height/ weight *	X		X				X			X				X	X	
Vital Signs	X		X				X			X				X	X	
Baseline Sx Checklist	X		X				X			X				X	X	
Physical/Neuro Exam	X						X			X				X	X	
Safety labs	X						X			X				X	X	
Inclusion/ Exclusion	X															
ADAS-Cog		X					X			X				X		
FDG PET scan-brain		X													X	
Lumbar puncture		X													X	
Isoprostane analysis **		X													X	
Dispense Study Drug			X				X			X						
Drug Accountability				X			X			X					X	

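### Adverse events are meant to guide dose selection, but no analysis by dose or exposure is planned, and raw counts would not compare the doses fairly

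*Combined protocol and SAP*

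**What the plan says.** **Use of the data.** Under Data analysis, Primary Aim: Safety, the plan looks at how often adverse events occur, how severe they are and whether the drug caused them. It then states: "This information will be used to guide dose selection and inform a more definitive safety and efficacy study". No breakdown by dose and no exposure denominator follows. In that paragraph a relation to dose is mentioned only for cognition.

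**The listing.** The Data Safety and Monitoring Plan has REDCap produce a list of grade 2 or higher events for the DSMB's quarterly review: "Each AE listed will include the grade, the type of event, and the potential relationship of the AE to the study intervention". Dose and onset date are not among the named items.

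**Departures from schedule.** Under Study Drug Administration, after a mild event the study clinician decides whether to continue and at what dosage. After an interruption of more than 10 days, "it will be titrated to the target dose with dose increases no more frequent than once a month".

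**Time at each dose.** The sections differ:
- Specific Aims: "Twenty subjects with probable AD will initiate treatment with 100 mg/day of R(+) pramipexole for one month", and then "If tolerated, the subjects will increase to 200 mg/day for one month and then 300 mg/day for the next 4 months".
- Study Drug Administration: one month at 100 mg/day and a second month at 200 mg/day, but the step to 300 mg/day is tied to a later point: "If at the end of four months of being on study drug, the participant is not experiencing side effects". The dose is then held at 300 mg/day, "where it will remain for the next 4 months". The same paragraph adds: "Subjects will be seen every two months for safety assessments prior to any dose escalation".
- Conclusions: escalation to 300 mg/day takes 4 months.
- Data analysis and End-of-Treatment Assessments: 6 months of treatment, with final assessments at week 24.

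**The concern.** Safety and tolerability is the primary aim. With one arm and escalation within each participant, dose and timing are the main handles for interpreting an event. If events are summarised over all doses together, the summary does not show which dose they arose on. If they are split by dose but left as raw counts, the dose held longest collects the most events even when the drug's event rate is the same throughout. Neither summary supports a fair comparison between doses, and the plan does not commit to anything better. The next study's dose choice is meant to draw on this summary.

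**Working it through.** **Check of the stated duration.** Specific Aims: 1 + 1 + 4 = 6 months, or 24 weeks at 4 weeks per month. This agrees with the 6 months and week 24 given elsewhere. Study Drug Administration read literally: 4 months before 300 mg/day + 4 months at it = 8 months. This does not agree. The plan gives no adverse event rate, so none can be reproduced.

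**Planned exposure.** Person-months at a dose = 20 participants × months at that dose, with no dropout. If the event rate is constant and dose has no effect, expected events are proportional to person-months, so the ratio of raw counts equals the ratio of exposures whatever the rate.

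| Reading (months at 100/200/300 mg/day) | Person-months | 300 vs 100 | 300 vs 200 | Share of events at 300 |
|---|---|---|---|---|
| Specific Aims, 1/1/4 | 20/20/80 | 4.0 | 4.0 | 80/120 = 67% |
| 300 mg/day after four months, treatment ends at week 24, 1/3/2 | 20/60/40 | 2.0 | 0.67 | 40/120 = 33% |
| One step at each two-monthly visit, 2/2/2 | 40/40/40 | 1.0 | 1.0 | 40/120 = 33% |
| Study Drug Administration taken literally, 1/3/4 (8 months) | 20/60/80 | 4.0 | 1.33 | 80/160 = 50% |
| Two-monthly steps, then four months, 2/2/4 (8 months) | 40/40/80 | 2.0 | 2.0 | 80/160 = 50% |

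On the Specific Aims schedule, the exposure at 300 mg/day is four times that at each lower dose taken singly, and 80/40 = 2.0 times the two combined.

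**Participants with at least one event.** The risk over a step is 1 − exp(−h × months), with h an assumed constant hazard. On the Specific Aims schedule:
- h = 0.02 per month: 0.077 at 300 mg/day against 0.020 at 100 mg/day, ratio 3.88 (unrounded risks).
- h = 0.10 per month: 0.330 against 0.095, ratio 3.46.

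Counting participants instead of events therefore barely changes the picture. Dividing events by person-months returns the ratio to 1.0.

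**Dropout.** If an assumed 10%, 20% or 30% leave before 300 mg/day, exposure there is 72, 64 or 56 person-months. The Specific Aims ratio to 100 mg/day becomes 3.6, 3.2 or 2.8.

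**Can dose be read from other records?** Not reliably from study week, given individual dosage decisions, re-titration and the conflicting schedule. Dispensing does not settle it either. Drug is dispensed at visits 1, 2 and 3, eight weeks apart, so on the Specific Aims schedule the first dispensing covers both the 100 and the 200 mg/day steps. The two-weekly calls are described as covering concurrent medications and adverse events, with no stated record of the current study dose.

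**The case against.** The strongest reply is that the listing is being asked to carry too much. It says what each entry will include, not that nothing else will appear. It is a monitoring aid for grade 2 or higher events, not the analysis data set, and the Data Management section leaves the adverse event forms and reports to be designed. The DSMB also has access to de-identified medical and other study records and, under its charter, receives all safety laboratory and clinical data on each participant. All of this stands. A reader might infer from the listing that dose at onset is not collected, or that the DSMB sees events without knowing the dose. The documents do not support either inference; they show only that the plan does not specify these items.

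The second reply is that the plan never proposes comparing raw counts between doses. Its stated goal is to establish that up to 300 mg/day is tolerated, and whether participants get through the escalation informs the next study without any such comparison. That also stands. It does not close the gap: the analysis section names dose selection as a use of event frequency and severity and leaves open how dose enters.

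Third, person-time does not make the doses comparable. Dose rises with time on drug, dosage may be altered after an event, and those who do not tolerate a step, or are removed after a grade 3 or higher event, contribute nothing at higher doses. This is correct, and it is why the comparison should be labelled descriptive.

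**Conclusion.** The concern holds as a gap in specification that is cheap to close. Event frequency and severity are to guide dose selection, yet no tabulation by dose and no exposure-adjusted rate is planned, and the one listing with named contents omits dose at onset and onset date.

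The size depends on which schedule applies. On the Specific Aims schedule, with 20 participants, no dropout and a constant event rate, raw counts at 300 mg/day would be four times those at each lower dose with no dose effect. On the other readings the ratio is 1.0 to 4.0 against 100 mg/day and 0.67 to 2.0 against 200 mg/day, so the distortion can vanish or, against 200 mg/day, reverse.

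Two stronger readings are tempting. One is that 300 mg/day is given for four times as long as a settled fact; the documents contradict one another on this. The other is that the safety data cannot inform dose choice at all; overall tolerability of the escalation still does. What is not supported is a fair comparison of raw counts across doses.

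**What to change.** 1. On the REDCap adverse event form, record onset date, actual daily dose at onset, and days since the last dose change or interruption. Show these items in the DSMB listing of grade 2 or higher events.
2. In Data analysis, Primary Aim: Safety, report events by actual dose at onset with the person-time accrued at that dose, alongside the raw counts.
3. State that the comparison across doses is descriptive, because dose rises with time on drug and because participants who do not tolerate a step, or are removed after a grade 3 or higher event, do not contribute at higher doses.
4. Reconcile Specific Aims, Study Drug Administration and Conclusions with each other and with the week 24 end of treatment, so that planned exposure at each dose is defined. Which schedule applies is for the sponsor and the investigator to settle.

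Cost: two or three database fields and one extra table, plus the text reconciliation. No new participant procedure is needed.
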